4.2.4.2 Analysis of primary variable

The MMRM analysis of the primary endpoint in the Evaluable analysis set will be considered the primary analysis.

The primary efficacy analysis will compare treatment groups (Total EBID vs. PBO) with respect to change in HbA1c from baseline Visit 3 (Week 0) to Visit 11 (Week 28) using the MMRM approach. The model will include change in HbA1c as the dependent variable and treatment, baseline HbA1c, background diabetes therapy strata (drug naïve, metformin only, SU only, and metformin + SU), week of visit, baseline HbA1c-by-week interaction and treatment-by-week interaction as the fixed effects. The variance - covariance structure to be used for this modelling will be unstructured (UN); if the model does not converge with unstructured variance – covariance matrix, then autoregressive order 1 (AR [1]) and heterogeneous autoregressive order 1 (ARH [1]) structures will be tried and the covariance structure will be decided based on model convergence status and the Akaike information criterion. The restricted maximum likelihood (REML) method will be used for parameter estimation. The least squares (LS) mean, 2-sided 95% confidence interval, and p-value of the difference in the change of HbA1c between the Total EBID and PBO groups at Visit 11 (Week 28) will be provided. The mean (SD) observed HbA1c at baseline and Week 28 will also be given by treatment group.

HbA1c data from post-baseline visits (including ED) will potentially be included in the MMRM analysis. In addition, if a patient’s last available measurement during the 28-week assessment period is from an unscheduled visit or ED visit, the value will be programmatically mapped to the next closest scheduled visit and potentially included in the MMRM analysis. See Section 4.1.3 for details on missing data handling and Section 4.2.4.1 for details on handling of data after IEs.

For patients who initiate rescue medication or discontinue IP and continue study participation, only data before initiation of rescue medication or up to and including date of discontinuation from IP will be included in the MMRM/ANCOVA analysis. If there is evidence that a measurement was taken prior to initiation of rescue medication, then this data will be included. If the measurement was taken on the date of initiation of rescue medication but time information is not available, then the measurement will be included. Data collected after discontinuation of IP will be excluded from analyses for all secondary efficacy endpoints.

Summaries and analysis of the primary endpoint will be performed in the Evaluable analysis set.

Assessment of homogeneity of treatment effect:

The homogeneity of treatment effect will be assessed by adding treatment by baseline interaction and treatment by strata interaction to the primary MMRM model as described in [Section 4.2.4.2](#). The same covariance structure as used for the primary analysis will be used for this model. The p-value for the interaction effects will be explored to identify the potential trend for non-homogeneity.

Descriptive summary of primary efficacy variable by visit

Actual, change and percent change from baseline values of HbA1c will be summarized using descriptive statistics by visit and treatment group. Plots of mean \pm standard error of mean for the change from baseline in HbA1c by visit and treatment group will be provided. Only OC summaries will be provided.

Subgroup analysis

The primary endpoint, change from baseline in HbA1c at week 28, will be summarized descriptively for subgroups of interest listed below. No statistical analyses will be conducted.

- Sex
- Age group: two different definitions.
 - Age (years) <10, 10 to 12, 13 to 16, >16
 - Age (years) <10, 10 to 17, and >17
- Race

Actual, change and percent change from baseline values of HbA1c will be summarized using descriptive statistics by visit and treatment group for each subgroup of the Evaluable analysis set. OC summaries will be provided.

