### **6.1.3. Randomization and Treatment Initiation (Visit 3)**

At Visit 3 (study baseline), patients should arrive at the study site after an overnight fast of at least 8 hours and should omit their morning study drug injection, oral antidiabetes medications, and concomitant medications prior to arriving so that fasting laboratory assessments can be performed. In addition, laboratory assessments for carcinoembryonic antigen (CEA) and calcitonin will be performed at baseline.

Patients will be randomly assigned to 1 of 3 treatment arms: exenatide 5 µg twice daily, exenatide 10 µg twice daily, or placebo twice daily in a double-blind manner. Patients randomized to placebo will be assigned to take the volume equivalent to exenatide 5 µg or to take the volume equivalent to exenatide 10 µg. However, the data for all placebo patients will be later combined into 1 group (regardless of injection volume) for analysis purposes. Patients will be randomized to treatment in the proportion of 2:2:1:1 (exenatide 5 µg twice daily; exenatide 10 µg twice daily; placebo volume equivalent of exenatide 5 µg twice daily; placebo volume equivalent exenatide of 10 µg twice daily, respectively) and stratified by screening HbA1c values ( $\leq 8\%$  and  $> 8\%$ ) as well as background diabetes therapy (drug naïve, metformin only, SU only and metformin+SU) to ensure a balanced distribution of patients within these strata across the treatments. Patients will receive injection pens of exenatide or placebo. Patients will be reinstructed on how to use their injection pen; however, they will not administer their first dose of the assigned therapy until the evening of Visit 3 (within 60 minutes before their evening meal). Dosing of patients participating in the pharmacokinetic addendum at Visit 3 will be altered from that in the main protocol. Patients will administer their first dose of the assigned therapy at Visit 3 (approximately 15 minutes before receipt of first meal at the clinic). Patients taking part in the pharmacokinetic addendum are not required to take an evening dose as per protocol. All injections of study drug (placebo and exenatide) will be SC into the abdomen.

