### 11.2. Statistical and Analytical Plans

#### 11.2.1. General Considerations

All of the data will be entered, verified, and archived at Amylin Pharmaceuticals, LLC or its delegate. All data listings, summaries, and analyses will be performed under the guidance and approval of the assigned statisticians. A detailed statistical analysis plan (SAP) will be developed before database lock. The full analysis set will use the intent-to-treat (ITT) principle and include the data from all randomized patients who received at least 1 dose of study drug.

Although, patients randomly assigned to placebo will be assigned to take the volume equivalent to 5 µg exenatide twice daily, or to take the volume equivalent to 10 µg exenatide twice daily, those patients will be combined into 1 group for analysis purposes.

Multiplicity adjustments for the primary analysis will be performed using Fisher Protected Testing procedure. No imputation of missing data will be performed with the exception of the last observation carried forward (LOCF) of post-baseline values in change from baseline to endpoint analyses. All tests of treatment effects will be conducted at a two-sided significance level of 0.05 unless otherwise stated.

Supportive analyses will be performed on the per-protocol analysis set. Per-protocol patients will be randomized to study drug, adhere to the inclusion/exclusion criteria, and have a Week 28 HbA1c measurement.

Any change to the data analysis methods described in the protocol will require an amendment ONLY if it affects the primary analysis. Any other change to the data analysis methods described in the protocol and the justification for making the change will be described in the SAP as well as the clinical study report.

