### **11.2.6. Primary Outcome and Methodology**

The primary outcome is the change in HbA1c from baseline to treatment endpoint at 28 weeks. The ITT analysis set will be used to demonstrate superiority of exenatide to placebo.

The method for the primary efficacy analysis will be a mixed model repeated measures (MMRM) ANCOVA under the assumption that data are missing at random (MAR). The model will include change in HbA1c as the dependent variable and treatment, screening HbA1c strata ( $\leq 8\%$  and  $> 8\%$ ), baseline HbA1c, background diabetes therapy strata (drug naïve, metformin, an SU, and a combination of metformin and an SU), week of visit, and treatment-by-week interaction as fixed effects and patient as the random effects. The plan for determining a covariance structure to be used for this model will be described in the SAP. All post-baseline measurements of the change in HbA1c will be included in the analysis with no imputation of missing data other than that inherent in the MMRM model. If the last efficacy measurement is collected at a visit for which the efficacy measurement is not planned to be collected, the measurement collected at the early termination visit will be mapped to the following planned visit. Using SAS® PROC MIXED, least squares (LS) means and 95% confidence interval will be produced from the model to estimate the magnitudes of treatment effects. The p-value for the overall test for differences among treatments will be obtained directly from the MMRM analysis. Pairwise comparisons between each exenatide treatment and placebo will be obtained from the MMRM model. Inferences will be based on the estimate of the treatment difference at Week 28. Superiority of exenatide treatment to placebo with regard to change in HbA1c will be concluded if the p-value adjusted using the Fisher Protected Testing procedure for at least one of the exenatide treatment arms is less than 0.05.

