1.2 Study design

This is a multicenter, double-blind, placebo-controlled, randomized, parallel, 3-arm trial. Approximately 195 adolescents, ages 10 to 17 years inclusive, with type 2 diabetes will be enrolled. The number of patients aged 17 years of age will be limited to no more than 10% of patients in each treatment arm. Patients will be naïve to antidiabetic agents, or they will be receiving oral treatment with metformin, an SU, or a combination of metformin and an SU at the time of enrolment. Randomization will be stratified by the patient’s background diabetes therapy and screening HbA1c. The study will commence with a 1-week, single-blind, injectable placebo lead-in period before patients are randomly assigned to add injectable exenatide or injectable placebo to their existing diabetes treatment. Patients will be randomly assigned to 1 of 3 treatment arms: exenatide 5 µg twice daily, exenatide 10 µg twice daily, or placebo twice daily (volume of injection equivalent to exenatide 5 µg or exenatide 10 µg). During the first 4 weeks after randomization, all patients assigned to treatment will receive exenatide 5 µg twice daily or equivalent placebo volume twice daily. A starting dose of exenatide 5 µg twice daily and titration to exenatide 10 µg twice daily has been shown to mitigate the incidence of nausea. At the end of 4 weeks post-randomization, patients assigned to the exenatide 10 µg twice daily treatment arm, or equivalent placebo volume, are then to increase their dose from 5 µg twice daily to 10 µg twice daily, or equivalent placebo volume. Study drug will be administered

[figure not shown]
within 60 minutes before morning and evening meals (or the 2 main meals of the day, approximately 6 hours or more apart) for 28 weeks.

All patients will be expected to participate in a simplified lifestyle modification program (LMP) throughout this study. The simplified lifestyle modification program will include both dietary education and physical activity components. At the clinic visits, the patients will meet with a registered dietitian (RD) or certified diabetes educator (CDE) who will review the patient's dietary history and physical activity record. The LMP will be reinforced at each visit.

Patients who have discontinued the study due to loss of glycemic control will be offered alternative antidiabetic therapy at the discretion of the investigator.

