As a sensitivity analysis, also in the Evaluable analysis set, the probabilities of patients reaching HbA1c targets of <7%, ≤6.5%, and <6.5% will be analyzed to Week 28 using the CMH procedure, with missing data imputed using MI pattern mixture model imputation. HbA1c and background diabetes therapy strata will serve as the stratification factors. The imputed HbA1c data for the sensitivity analysis of the primary endpoint will be used for this analysis.

Similar outputs (bar chart including p-values and summary of the numbers and percentage of patients having HbA1c goals by visit and treatment group) will be produced for the Evaluable analysis set for this sensitivity analysis.

Change in body weight, FSG and FSI from baseline Visit 3 (Week 0)

The same MMRM approach (as used for the primary analysis) will be used to analyze the change in body weight from baseline Visit 3 (Week 0) to Week 28, and each intermediate visit. Baseline body weight will replace baseline HbA1c and screening HbA1c strata will be included in these models.

Since only baseline and endpoint FSG and FSI measurements are collected, these endpoints will be analyzed by multiple imputation based on the assumption that missing data are MAR via the following steps:

Step 1: Non-monotone missing data (expected to be infrequent) will be imputed using the MCMC option of SAS PROC MI with treatment, baseline FSG/FSI, screening HbA1c strata (≤8% and >8%) and background diabetes therapy strata (drug naïve, metformin only, SU only, and metformin +SU) and value of the endpoint at each visit. This will create a monotone missing pattern in the dataset within each treatment group. This step will create 1000 imputed datasets.

Step 2: After a monotone missing pattern is created for the data, PROC MI using MONOTONE REGRESSION will be used to impute missing post-baseline values. The covariates used in the model will be treatment, baseline FSG/FSI, screening HbA1c strata (≤8% and >8%) and background diabetes therapy strata (drug naïve, metformin only, SU only, and metformin +SU) and value of the endpoint at each visit. This is MAR imputation.

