6 CHANGES OF ANALYSIS FROM PROTOCOL

The CSP does not specify eGFR as an endpoint, nor is it provided by the laboratory. However, since eGFR could provide important information it will be derived and analyzed as stated in Section 4.2.4.5 of this SAP.

In addition to the protocol-specified analysis, hypoglycemia will be summarized by baseline sulfonylurea use (yes/no) and treatment.

No Generalized Linear Mixed Model (GLMM) analysis will be done using the binary HbA1c outcome (achieved vs. not achieved HbA1c goal) as the dependent variable.

No per-protocol analysis for supportive analyses will be done.

Due to the lack of data and extent of missing data, efficacy analyses will be pooled across the 5 µg and 10 µg twice daily exenatide doses for statistical testing (Total EBID). Thus, the Fisher Protected Testing produced for the primary analysis will not be required.

For the analysis of SMBG, pre and post measurement for the same meal (lunch/dinner) is changed to be generically 2 main meals (i.e. allowing breakfast) and changed to allow data from consecutive days to be used (as many patients had only consecutive days data recorded).

Due to lack of data, plasma exenatide concentrations and antibodies will only be listed.

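### The SAP's primary MMRM omits the screening HbA1c stratum that randomization used and the protocol model contains, and Section 6 does not list the omission; the numerical effect is very small

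*SAP*

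**What the plan says.** **Design.** Protocol 6.1.3 has patients "stratified by screening HbA1c values", cut at 8%, and by four levels of background therapy. Protocol 8.3 repeats this. SAP 1.2 agrees: "Randomization will be stratified by the patient’s background diabetes therapy and screening HbA1c".

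**Protocol primary model (11.2.6).** "The model will include change in HbA1c as the dependent variable and treatment, screening HbA1c strata". The list goes on with baseline HbA1c, background therapy strata, week and treatment-by-week as fixed effects, and patient as a random effect.

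**SAP primary model (4.2.4.2).** The terms begin "treatment, baseline HbA1c, background diabetes therapy strata (drug naïve, metformin only, SU only, and metformin + SU), week of visit" and end "baseline HbA1c-by-week interaction and treatment-by-week interaction as the fixed effects". No HbA1c stratum appears.

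**SAP body-weight model (4.2.4.4).** "Baseline body weight will replace baseline HbA1c and screening HbA1c strata will be included in these models". The stratum is brought in as an addition, which confirms that its absence from the primary model is not a slip of transcription.

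**Rule on changes (Protocol 11.2.1).** "Any change to the data analysis methods described in the protocol will require an amendment ONLY if it affects the primary analysis". Other changes are to be described and justified in the SAP and the study report.

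**SAP Section 6.** The only listed change to the primary analysis is the pooling of the two doses: "Thus, the Fisher Protected Testing produced for the primary analysis will not be required". The SAP amendment history does not mention covariates either.

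**The concern.** A trial is normally analysed with the factors by which it was randomized, so that the model reflects the restriction that the design imposed. Here the protocol made that choice for the primary endpoint and the SAP reversed it without a reason.

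Three things are at stake:

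- **Traceability.** The change touches the primary model, and the supplied protocol, amendment (e), still has the stratum in it. An unlisted change of that kind invites questions even when it is harmless.
- **No planned check.** No planned analysis of change in HbA1c uses the protocol's covariates. The by-visit, sensitivity and supplementary analyses all build on the 4.2.4.2 model, and the protocol's supportive LOCF ANCOVA of HbA1c, which carried the stratum, is not in the SAP. A reader could not see from the planned output that the omission makes no difference.
- **A mismatch downstream.** The sensitivity CMH for the HbA1c goals stratifies by HbA1c and background therapy, but reuses HbA1c values imputed by models without the HbA1c stratum.

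**Working it through.** **1. Where the stratum appears.**

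| Analysis | Continuous baseline HbA1c | Screening HbA1c stratum |
|---|---|---|
| Protocol 11.2.6, primary MMRM | yes | yes |
| SAP 4.2.4.2, primary MMRM | yes | no |
| SAP 4.2.4.3, Steps 1 to 3 | yes | no |
| SAP 4.2.4.4, HbA1c by visit | yes | no |
| SAP 4.2.4.4, HbA1c-goal CMH | no | yes |
| SAP 4.2.4.4, body weight MMRM | no | yes |
| SAP 4.2.4.4, FSG and FSI ANCOVA | no | yes |
| SAP 4.2.5.4, eGFR ANCOVA | no | yes |

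The pattern is regular: analyses with continuous baseline HbA1c drop the stratum, and those without it keep the stratum. The BMI and percentile models in SAP 4.2.4.5 only point back to the primary approach and do not say which HbA1c term they carry.

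**2. What Section 6 lists.** eGFR, hypoglycemia by sulfonylurea use, no GLMM, no per-protocol analysis, dose pooling without the Fisher procedure, SMBG handling, and PK and antibodies listed only. No entry concerns the covariates of the primary model.

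**3. The plan's own power figure.** SAP 1.3 gives about 87% for 122 patients at 2:1, difference 0.6, SD 1.0, two-sided 5%.

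- SE = SD × √(1/n₁ + 1/n₂) = 1.0 × √(1/40.67 + 1/81.33) = 0.192.
- Power ≈ Φ(0.6/0.192 − 1.96) = Φ(1.164) = 87.8%. With the noncentral t it is 87.3%.

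The figure reproduces. The formula has no covariate term, so the effect of the stratum has to be simulated.

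**4. With and without the stratum.** The simulation is a single-endpoint ANCOVA with N = 122, 2:1 within HbA1c stratum, true effect −0.6, residual SD 1 and 3,000 trials per row. Assumptions not in the documents: screening HbA1c mean 8.2 and SD 1.1 (held within 6.5 to 10.5), baseline slope −0.3, and the first two columns below. Background therapy and missing data are left out.

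| Extra stratum effect | Screening-to-baseline SD | SE without | SE with | Change | Power without | Power with |
|---|---|---|---|---|---|---|
| 0 | 0.3 | 0.1923 | 0.1928 | +0.3% | 87.3% | 87.1% |
| 0 | 0.6 | 0.1929 | 0.1934 | +0.3% | 88.0% | 88.1% |
| 0.3 | 0.3 | 0.1937 | 0.1934 | −0.2% | 86.5% | 86.7% |
| 0.3 | 0.6 | 0.1941 | 0.1935 | −0.3% | 86.1% | 86.0% |
| 0.5 | 0.3 | 0.1949 | 0.1930 | −1.0% | 86.3% | 87.1% |
| 0.5 | 0.6 | 0.1958 | 0.1932 | −1.3% | 86.5% | 87.1% |

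The mean estimate is between −0.600 and −0.607 in every row under both models. The largest power gap is 0.8 points. A second simulation (4,000 stratified trials, assumed screening-to-baseline correlation 0.85) gave SE 0.1845 without and 0.1837 with the stratum: 0.0008/0.1845 = 0.4%.

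**The case against.** The best case for the SAP is that the stratum is a two-level cut of an HbA1c taken about three weeks before baseline. The model keeps the continuous baseline value and adds its interaction with week, so most of what the stratum carries is already adjusted for. The table in the working supports this: the SAP seems to apply a substitution rule, with one HbA1c term or the other. The amendment history also says openly that the SAP was fully rewritten and aligned with another study where appropriate.

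Most of that stands. It explains why the effect is small. It does not supply the missing entry: the SAP states no such rule, and the protocol chose to carry both terms.

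Three stronger readings are tempting, and the documents do not support them:

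- *The primary test is biased or underpowered.* The estimate is unchanged and power moves by under 1 point in every scenario tried.
- *All secondary models keep the stratum, so the SAP contradicts itself.* The by-visit HbA1c analysis is secondary and omits it, in line with the primary model.
- *Restoring the term returns the protocol's model.* It does not. The SAP also adds baseline-by-week, uses a covariance structure in place of the patient random effect, pools the doses and analyses the Evaluable set.

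**Conclusion.** The point holds as one of fidelity to the design and the protocol. A randomization factor named in the protocol's primary model is absent from the SAP's primary model and the imputation built on it, with no entry or reason in Section 6. Under Protocol 11.2.1 a change affecting the primary analysis calls for an amendment. The supplied protocol text contains none on this, though a later amendment outside these documents cannot be excluded.

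The size is very small: about 1% of the standard error at most (1.3% in the most extreme scenario), under 1 point of power, and no shift in the estimate. Those figures rest on assumed screening-to-baseline relationships and on a simpler model than the planned MMRM. The effect of the mismatch in the HbA1c-goal sensitivity analysis was not quantified; since those imputation models contain baseline HbA1c, it too is likely to be small. This is an inexpensive improvement and does not threaten the primary conclusion.

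**What to change.** - In SAP 4.2.4.2, add screening HbA1c stratum (≤8%, >8%) as a fixed effect in the primary MMRM. The by-visit HbA1c analysis then inherits it.
- Add the same term to Steps 1 to 3 of SAP 4.2.4.3. This also aligns the imputation with the HbA1c-goal sensitivity CMH.
- State that the stratum is the one used for randomization, because SAP Table 1 (item 5) foresees patients assigned to the wrong IVRS stratum.
- In SAP 4.2.4.2, name the strata meant in the treatment-by-strata homogeneity check.
- In SAP Section 6, list the remaining differences from the protocol's primary model with reasons: at least the baseline-by-week term, the covariance structure in place of the patient random effect, and the Evaluable set.

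The cost is one degree of freedom and no new data. It weighs most in Step 2, where the regression is fitted on placebo patients, about 122/3 ≈ 41 at most. The parameters rise from 6 (intercept, baseline HbA1c, three for therapy, prior-visit HbA1c) to 7, so the residual degrees of freedom fall from about 35 to 34.

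If the sponsor prefers to leave the stratum out, the minimum is a Section 6 entry with the reason, handled as Protocol 11.2.1 requires, and a sensitivity analysis with the protocol's covariates.
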